Appendix 5 Description of the iRECIST Process for Assessment of Disease Progression

● Assessment at Screening and Prior to RECIST 1.1 Progression

Until radiographic Progressive Disease (PD) based on RECIST 1.1, there is no distinct iRECIST assessment.

● Assessment and Decision at RECIST 1.1 Progression

For subjects who show evidence of radiological PD by RECIST 1.1 as determined by the investigator, the investigator will decide whether to allow a subject to continue to receive study treatment until repeat imaging is obtained (using iRECIST for subject management (see Table A5:1)). This decision by the investigator should be based on the subject's overall clinical condition.

Tumor flare may manifest as any factor causing radiographic progression per RECIST 1.1, including:

- Increase in the sum of diameters of target lesion(s) identified at baseline to $\geq 20\%$ and ≥ 5 mm from nadir

Note: the iRECIST publication uses the terminology "sum of measurements", but "sum of diameters" will be used in this protocol, consistent with the original RECIST 1.1 terminology.

- Unequivocal progression of nontarget lesion(s) identified at baseline
- Development of new lesion(s)

iRECIST defines new response categories, including iUPD (unconfirmed progressive disease) and iCPD (confirmed progressive disease). For purposes of iRECIST assessment, the first visit showing progression according to RECIST 1.1 will be assigned a visit (overall) response of iUPD, regardless of which factors caused the progression.

At this visit, target and nontarget lesions identified at baseline by RECIST 1.1 will be assessed as usual.

New lesions will be classified as measurable or nonmeasurable, using the same size thresholds and rules as for baseline lesion assessment in RECIST 1.1. From measurable new lesions, up to 5 lesions total (up to 2 per organ), may be selected as New Lesions -Target.

The sum of diameters of these lesions will be calculated and kept distinct from the sum of diameters for target lesions at baseline. All other new lesions will be followed qualitatively as New Lesions - Non-target.

● Assessment at the Confirmatory Imaging

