On the confirmatory imaging, the subject will be classified as progression confirmed (with an overall response of iCPD), or as showing persistent unconfirmed progression (with an overall response of iUPD), or as showing disease stability or response (immune-based stable disease/immune-based partial response/immune-based complete response [iSD/iPR/iCR]).

Confirmation of Progression

Progression is considered confirmed, and the overall response will be iCPD, if ANY of the following occurs:

- Any of the factors that were the basis for the initial iUPD show worsening
 - For target lesions, worsening is a further increase in the sum of diameters of ≥ 5 mm, compared to any prior iUPD time point
 - For nontarget lesions, worsening is any significant growth in lesions overall, compared to a prior iUPD time point; this does not have to meet the “unequivocal” standard of RECIST 1.1
 - For new lesions, worsening is any of these:
 - An increase in the new lesion sum of diameters by ≥ 5 mm from a prior iUPD time point
 - Visible growth of new nontarget lesions
 - The appearance of additional new lesions
- Any new factor appears that would have triggered Progressive Disease (PD) by RECIST 1.1

Persistent iUPD

Progression is considered not confirmed, and the overall response remains iUPD, if:

- None of the progression-confirming factors identified above occurs AND
- The target lesion sum of diameters (initial target lesions) remains above the initial PD threshold (by RECIST 1.1)

Additional imaging for confirmation should be scheduled 4 to 8 weeks from the imaging on which iUPD is seen. This may correspond to the next visit in the original visit schedule. The assessment of the subsequent confirmation imaging proceeds in an identical manner, with possible outcomes of iCPD, iUPD, and iSD/iPR/iCR.

Resolution of iUPD

Progression is considered not confirmed, and the overall response becomes iSD/iPR/iCR, if:

- None of the progression-confirming factors identified above occurs, AND
- The target lesion sum of diameters (initial target lesions) is not above the initial Progressive Disease (PD) threshold.

The response is classified as iSD or iPR (depending on the sum of diameters of the target lesions), or iCR if all lesions resolve.

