In this case, the initial iUPD is considered to be pseudo-progression, and the level of suspicion for progression is “reset.” This means that the next visit that shows radiographic progression, whenever it occurs, is again classified as iUPD by iRECIST, and the confirmation process is repeated before a response of iCPD can be assigned.

● Management Following the Confirmatory Imaging

If repeat imaging does not confirm Progressive Disease (PD) per iRECIST, as assessed by the investigator, and the subject continues to be clinically stable, study treatment may continue and follow the regular imaging schedule. If Progressive Disease (PD) is confirmed, subjects will be discontinued from study treatment.

NOTE: If a subject has immune confirmed progressive disease (iCPD) as defined above, but the subject is achieving a clinically meaningful benefit, an exception to continue study treatment may be considered following consultation with the Sponsor. In this case, if study treatment is continued, tumor imaging should continue to be performed following the intervals as outlined in Section **9.1.1**

● ***Detection of Progression at Visits After Pseudo-progression Resolves***

After resolution of pseudo-progression (i.e., achievement of iSD/iPR/iCR), iUPD is indicated by any of the following events:

- **Target lesions**
 - Sum of diameters reaches the Progressive Disease (PD) threshold ($\geq 20\%$ and ≥ 5 mm increase from nadir) either for the first time, or after resolution of previous pseudo-progression. The nadir is always the smallest sum of diameters seen during the entire trial, either before or after an instance of pseudo-progression.
- **Non-target lesions**
 - If nontarget lesions have never shown unequivocal progression, their doing so for the first-time results in iUPD.
 - If nontarget lesions have shown previous unequivocal progression, and this progression has not resolved, iUPD results from any significant further growth of nontarget lesions, taken as a whole.
- **New lesions**
 - New lesions appear for the first time
 - Additional new lesions appear
 - Previously identified new target lesions show an increase of ≥ 5 mm in the new lesion sum of diameters, from the nadir value of that sum
 - Previously identified nontarget lesions show any significant growth

If any of the events above occur, the overall response for that visit is iUPD, and the iUPD evaluation process (see Assessment at the Confirmatory Imaging above) is repeated.

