Progression must be confirmed before iCPD can occur.

The decision process is identical to the iUPD confirmation process for the initial Progressive Disease (PD), with one exception: if new lesions occurred at a prior instance of iUPD, and at the confirmatory imaging the burden of new lesions has increased from its smallest value (for new target lesions, the sum of diameters is ≥ 5 mm increased from its nadir), then iUPD cannot resolve to iSD or iPR. It will remain iUPD until either a decrease in the new lesion burden allows resolution to iSD or iPR, or until a confirmatory factor causes iCPD.

Additional details are provided in the iRECIST publication (Seymour, et al., 2017).

Table A5:1. Imaging and Treatment after First Radiologic Evidence of Progressive Disease in Subjects Receiving FLX475 and Pembrolizumab

● ***Clinical stability is defined as the following:***

- Absence of symptoms and signs indicating clinically significant progression of disease

[figure not shown]
- No decline in ECOG performance status
- No requirements for intensified management, including increased analgesia, radiation, or other palliative care

	Clinically Stable		Clinically Unstable	
	Imaging	Treatment	Imaging	Treatment
First radiologic evidence of PD by RECIST 1.1	Repeat imaging at 4 to 8 weeks to confirm PD.	May continue study treatment at the investigator's discretion while awaiting confirmatory tumor imaging by site by iRECIST.	Repeat imaging at 4 to 8 weeks to confirm PD per investigator's discretion only.	Discontinue treatment
Repeat tumor imaging confirms PD (iCPD) by iRECIST per investigator assessment	No additional imaging required.	Discontinue treatment (exception is possible upon consultation with Sponsor).	No additional imaging required.	Not applicable
Repeat tumor imaging shows iUPD by iRECIST per investigator assessment	Repeat imaging at 4 to 8 weeks to confirm PD. May occur at next regularly scheduled imaging visit.	Continue study treatment at the investigator's discretion.	Repeat imaging at 4 to 8 weeks to confirm PD per investigator's discretion only.	Discontinue treatment

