### 12.1 Tumor Assessment

Best overall response is the best response recorded from the treatment start date until the earliest of disease progression or last evaluable tumor assessment before events such as start of new anticancer therapy, death, lost to follow-up, etc. Objective response rate (ORR) is defined as the proportion of subjects whose confirmed best overall response is either Complete Response (CR) or Partial Response (PR) according to RECIST version 1.1. Disease control rate (DCR) is defined as the proportion of subjects with confirmed best overall response of CR, PR or SD according to RECIST version 1.1.

The hierarchy used to determine best overall response is CR>PR>SD>PD. [REDACTED]

The progression date is the earliest date among all images of PD lesion. If a subject does not experience PD in one disease assessment, his/her non-PD date will be the latest date among all images of the disease assessment.

Overall best response categories (including: CR, PR, PD, SD), ORR and DCR will be summarized (categorical descriptive analysis), together with the two-sided exact (Clopper-Pearson) 95% confidence intervals.

Based on the cumulative data about ORR along with prior assumption at each stage, posterior probability of ORR  $\geq 15\%$  for cohort 1 and ORR  $\geq 30\%$  for cohort 2 would be computed to determine go/no-go decision of the next stage. This cumulative data analysis will be implemented only if at least one response is observed from stage 1 of each cohort.

According to iRECIST, Best Overall Response (iBOR) of complete response (CR/iCR), partial response (PR/iPR), stable disease (SD/iSD), Progressive disease (iPD) or unevaluable (iUE) will be derived. iORR, iDCR, iTTR, iDoR and iPFS will be analyzed in the same manner as used analyses in accordance with RECIST 1.1. iPD is defined as the time point of first iUPD without subsequent iSD, iPR or iCR before study treatment discontinuation.

For the sum of diameter in target lesion, percent change from baseline at each scheduled tumor assessment time-point and maximal tumor shrinkage from baseline during the study will be summarized.

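### A first iUPD caused only by a new or non-target lesion cannot persist under Appendix 5: if the lesion is unchanged the scan becomes iSD or iPR, and that iUPD stops counting for iPFS

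*Protocol*

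**What the plan says.** Under Appendix 5, the first visit that meets RECIST 1.1 progression, through target growth, non-target progression or a new lesion, "will be assigned a visit (overall) response of iUPD, regardless of which factors caused the progression".

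The confirmatory scan then has three possible outcomes.

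- **iCPD**, if a causal factor worsens or a new progression factor appears. The non-target criterion is "For nontarget lesions, worsening is any significant growth in lesions overall, compared to a prior iUPD time point". One of the new-lesion criteria is "An increase in the new lesion sum of diameters by ≥ 5 mm from a prior iUPD time point"; visible growth of new non-target lesions and further new lesions also count.
- **Persistent iUPD**, which needs two things: "None of the progression-confirming factors identified above occurs AND" an initial target sum that is still above the progression threshold.
- **Resolution** to iSD, iPR or iCR. The first condition is the same, and the second is "The target lesion sum of diameters (initial target lesions) is not above the initial Progressive Disease (PD) threshold". The target sum decides between iSD and iPR. Only iCR requires every lesion to have resolved.

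After resolution, "the initial iUPD is considered to be pseudo-progression" and the suspicion of progression is reset. For a later episode only, resolution is blocked if "the burden of new lesions has increased from its smallest value"; a decrease in that burden lifts the block.

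Protocol 11.4.2 and SAP 12.1 share one definition: "iPD is defined as the time point of first iUPD without subsequent iSD, iPR or iCR before study treatment discontinuation". Both analyse the iRECIST endpoints in the same way as their RECIST 1.1 counterparts.

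**The concern.** The trigger for iUPD looks at all three lesion types. Once worsening has been ruled out, the test for whether it persists looks at one. When a new metastasis or a non-target lesion was the whole reason for the iUPD, that test does not examine the reason. The lesion can be exactly as it was, and the episode is still recorded as pseudo-progression.

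The SAP takes these categories as they stand, so the classification carries into the endpoints. The direction is one-sided: iPFS can only get later or become censored, and iDCR, iORR and iDoR can only improve. A reader who compares iPFS with RECIST 1.1 PFS would attribute the gap to true pseudo-progression, when part of it may come from the rule.

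**Working it through.** The plan gives no figure on this point, so there is none to reproduce. The check is a trace of the rule.

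**Step 1: follow a first iUPD caused only by a new or non-target lesion.** At the iUPD visit the target sum was not above threshold.

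| State at the confirmatory scan | Appendix 5 result | First iUPD counts as iPD? |
|---|---|---|
| Causal lesion worse, or a further new lesion | iCPD | Yes |
| Target sum now above threshold (a new factor) | iCPD | Yes |
| Causal lesion unchanged, target sum not above threshold | iSD or iPR | No |
| Causal lesion gone, target sum not above threshold | iSD, iPR or iCR | No |

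Persistent iUPD does not appear. The target sum cannot remain above a threshold it had not crossed, and crossing it now gives iCPD.

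**Step 2: enumerate all states.** The target sum has 3 states: not above, above without further worsening, above with further worsening. A causal non-target or new lesion has 3: resolved, unchanged, worse. A lesion type that was not a cause has 2: nothing to report, or newly progressing. For example, non-target only gives 3 × 3 × 2 = 18 states.

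| Cause of iUPD | States | iCPD | Resolved | Persistent iUPD |
|---|---|---|---|---|
| Non-target only | 18 | 16 | 2 | 0 |
| New lesion only | 18 | 16 | 2 | 0 |
| Non-target and new | 27 | 23 | 4 | 0 |
| Target only | 12 | 10 | 1 | 1 |
| Target and new | 18 | 14 | 2 | 2 |
| Target and non-target | 18 | 14 | 2 | 2 |
| All three | 27 | 19 | 4 | 4 |

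These counts show which outcomes can be reached. They are not probabilities. Persistent iUPD is empty exactly where the target lesions played no part.

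**Step 3: effect on iPFS.** Assume an iUPD at week 6 from a new lesion, and the lesion unchanged at week 12 on treatment. Week 12 is iSD or iPR, so week 6 is not an iPD. On the six-weekly schedule the earliest later unresolved iUPD is week 18, which is 18 − 6 = 12 weeks later. Death before then would be the event; with neither, the subject is censored at the last evaluable scan. Had week 12 stayed iUPD, with no later iSD, iPR or iCR on treatment, the event would be at week 6.

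**Step 4: effect on the other endpoints.**

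- iDCR changes only for a subject with no qualifying SD or PR before the iUPD, because best response keeps the earlier result and iBOR pools SD with iSD and PR with iPR (SAP 12.1).
- iORR changes only if an iPR or iCR is confirmed. Protocol 9.1.2.2 asks for repeat imaging at least 4 weeks later.
- iDoR lengthens for a subject who had already responded.

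**Step 5: size.** One subject is 1/30 = 3.3 points in a cohort of 30, or 1/60 = 1.7 points at the Cohort 1 maximum, where iDCR or iORR changes at all. The documents give no rate for progression driven only by new or non-target lesions, or for such lesions staying unchanged. Purely as assumptions per 30 subjects, take 24 RECIST progressions, 40–60% of them driven only by new or non-target lesions, half rescanned on treatment, and 10–30% unchanged:

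- low: 24 × 0.4 × 0.5 × 0.1 = 0.48 subjects
- high: 24 × 0.6 × 0.5 × 0.3 = 2.16 subjects

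This range counts subjects who lose the first iUPD date. Those who change iDCR or iORR are a subset.

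**The case against.** The strongest reply is that the rule is deliberate and coherent. Resolution has two joint conditions, and the first checks non-target and new lesions for worsening. Appendix 5 also foresees a resolved subject whose non-target progression has not itself gone away, and says what would trigger the next iUPD. Limiting the new-lesion block to later episodes leaves no gap for growth at a first, new-lesion iUPD, since worsening as Appendix 5 defines it is already iCPD. Protocol 9.1.3 and Appendix 5 refer to the iRECIST publication for detail. The endpoints are secondary and descriptive, no formal testing is planned, and RECIST 1.1 results are reported alongside.

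Most of this stands, and it rules out several stronger readings:

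- *Resolution rests on target lesions alone.* It does so only after worsening of every lesion type has been excluded. The lesion must be present and not worse; mere presence is not enough.
- *The iPFS event is deleted.* Only the first iUPD date is lost. A later unresolved iUPD or death still counts. Without an iSD, iPR or iCR scan before treatment discontinuation, the first iUPD counts as well.
- *Every reclassified subject adds to iDCR or iORR.* Earlier SD or PR, and the confirmation requirement, prevent that.
- *Appendix 5 contradicts itself, or departs from published iRECIST.* The first is not so. The second cannot be judged from these documents.

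The reply does not remove the unchanged-lesion case. The rule is consistent, but it still labels as pseudo-progression an episode whose cause is unaltered, and the SAP carries that label into iPFS.

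**Conclusion.** The point holds for one defined group: subjects whose first iUPD came only from a new or non-target lesion, who are rescanned on treatment, whose lesion is unchanged, and whose target sum is not above threshold. Appendix 5 gives them iSD or iPR, and the iPD definition drops the first iUPD from iPFS. The bias runs one way, towards more favourable iRECIST results.

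The number of subjects cannot be derived from the plan. The range of about 0.5 to 2.2 per 30 depends wholly on the assumed inputs and should not be cited as an estimate. A reader might infer that the main results are in doubt, but the documents do not support that: primary ORR, RECIST 1.1 PFS and the ORR-based posterior rule all use RECIST 1.1 and are untouched. The point deserves correction because it affects named secondary endpoints systematically and the repair is small.

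**What to change.** Add a derivation rule to SAP 12.1, applying only to iBOR, iORR, iDCR, iTTR, iDoR and iPFS:

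- An iUPD caused by a new or non-target lesion stays iUPD while the causal lesion is present and unchanged, meaning neither worse by the Appendix 5 criteria nor improved as described next.
- It resolves to iSD or iPR only when the target sum is not above threshold and, for each causal factor, the new-lesion burden has decreased or the non-target progression is no longer unequivocal.
- iCR still requires all lesions to have resolved.

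Requiring new lesions to disappear would go too far, because Appendix 5 already accepts a decrease in new-lesion burden as permitting resolution at a later episode.

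The cost is a derivation from lesion-level data instead of the recorded visit response, and slightly less favourable iRECIST results. Appendix 5 already has the target, non-target and new lesions assessed, with a separate sum for measurable new lesions.

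Appendix 5 and Table A5:1 also govern imaging and treatment, and the table handles iUPD differently from iSD, iPR and iCR. The sponsor should reconcile that text with the derivation, or state that the endpoint category and the management category may differ. No clinical rule is proposed here.

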Appendix 6 Prohibited Medications and Therapies

The following is a list of all medications, therapies (including procedures) that are prohibited while the subject is enrolled in this study. Subjects receiving any of these medications at study entry should discontinue the treatment or be switched to a different medication with similar pharmacology prior to starting study treatment. Subjects who receive any of these medications during the Treatment Phase must discontinue study treatment.

Table A6:1. Medications that potentially prolong the QT interval

A list of medications known to cause QTc interval prolongation is provided in the table below and is also available at the following link: <https://crediblemeds.org/index.php/drugsearch>. This list is not all-inclusive.

Compounds	Compound Half-Life	Possible Washout Period – Hours	Possible Washout Period - Days
Alfuzocin	~10 hours		7
Amantadine	17 +/- 4 hours (10–25)		4
Amiodarone (cordarone)	58 days (15–142) 36 days (active metabolite)		180
Amitriptyline*	> 24 hours, wide interpatient variability		
Arsenic trioxide	Not characterized		
Azithromycin	40 hours		
Bepridil	42 hours (26-64)		10
Chloral hydrate	Readily converted to Trichloroethanol (active metabolite T1/2 = 7–10 hours)	48	
Chloroquine	Prolonged (days to weeks)		
Chlorpromazine	30 +/- 7 hours		
Clarithromycin	Non-linear PK3-4 hr (250mg Q12) 5–7 hr (500 mg Q12)	36	
Cloroquine	6 to 60 days; mean 20 days		
Desipramine*	> 24 hours, wide interpatient variability		
Disopyramide	6.7 hr (4-10)	36	
Dofetilide	10 hours	48	
Dolesetron	8.1 hours		
Domperidone	7-8 hours	48	

Compounds	Compound Half-Life	Possible Washout Period – Hours	Possible Washout Period - Days
Doxepin*	> 24 hours, wide interpatient variability		
Droperidol	2.2 hours	10	
Erythromycin	*Each salt form has different Half-Life*		
Felbamate	20–23 hours		5
Flecainide	20 hours (12–27)		5
Foscarnet	87.5 +/-41.8 hours *distribution and release from bone*		20
Fosphenytoin	12–29 hours		6
Gatifloxacin	7–14 hours	48	
Gemifloxacin	7 hours	48	
Grepafloxacin	16 hours		3
Halofantrine	6–10 days (variable among individual)		45
Haloperidol	18 +/-5 hours		5
Ibutilide	6 hours (2–12) *variable among subject*	36	
Imipramine*	> 24 hours, wide interpatient variability		
Indapamide	14 hours (biphasic elimination)		3
Isardipine	8 hours (multiple metabolites)	48	
Levofloxacin	6–8 hours	48	
Levomethadyl	Multiple compartment PK with active metabolite 2.6 days for LAAM, 2 day for nor-LAAM, 4 day for dinor-LAAM		20
Lithium	24 hours (10–50)		7
Mesoridazine	24–48 hours (animal study)		10
Methadone	15–30 hours		7
Moexipril/HCTZ	2–9 hour (include active metabolite) for moexipril; 5.6–14.8 hours for HCTZ	48	
Moxifloxacin	12 +/-1.3 hours	72	
Naratriptan	6 hours	36	
Nicardipine	~ 2-hour post IV infusion	12	

Compounds	Compound Half-Life	Possible Washout Period – Hours	Possible Washout Period - Days
Nortriptyline*	> 24 hours, wide interpatient variability		
Octreotide	1.7 hours	12	
Ofloxacin	5 to 7.5 hours		2
Ondansetron	4 hours (IV/IM); 3 hours (PO)		1 to 3
Pentamidine	6.4 +/- 1.3 hours	36	
Pimozide	55 hours		10
Procainamide	3–4 hours for PA and NAPA (active metabolite)	24	
Protriptyline*	> 24 hours, wide interpatient variability		
Quetiapine	6 hours	36	
Quinidine	6-8 hours in adult; 3–4 hours in children	36	
Quinine	4–5 hours		
Risperidone	3–20 hours (extensive to poor metabolizer) 9-hydroxyrisperidone (active metabolite) T1/2 = 21-30 hours (extensive to poor metabolizer)		4
Salmeterol	5.5 hours (only one datum)	36	
Sotalol	12 hours	72	
Sparfloxacin	20 hours (16–30)		4
Sumatriptan	2.5 hours	12	
Tacrolimus	~34 hours in healthy; ~19 hours in Kidney transplant		7
Tamoxifen	5–7 days (biphasic)		30
Telithromycin	2-3 hours	24	
Thioridazine	20–40 hours (Phenothiazines)		7
Tizanidine	2.5 hours	12	
Vardenafil	4 to 5 hours		
Venlaflaxine	5 +/- 2 hours for parent comp. 11 +/- 2 hours for OVD (active metabolite)	60	
Ziprasidone	7 hours	36	
Zolmitriptan	2.8–3.7 hours (higher in female)	18	

*Weakly associated with Torsades de pointes and/or QT prolongation but that are unlikely to be a risk for Torsades de pointes when used in usual recommended dosages and in patients without other risk factors (e.g., concomitant QT prolonged drugs, bradycardia, electrolyte disturbances, congenital long QT syndrome, concomitant drugs that inhibit metabolism).

Source: 1. *Physician's Desk Reference 2002*; 2. *Facts and Comparison (update to June 2005)*; 3. *The Pharmacological Basis of Therapeutics 9th Edition*, 1999.

Table A6:2. Known Strong Cytochrome P450 (CYP)3A4 Inhibitors or Inducers

Medication Type	Drug Names
CYP3A4 Inhibitors	
Strong inhibitors	boceprevir, clarithromycin, conivaptan, grapefruit-containing products, indinavir, lopinavir, mibepradil, nefazodone, nelfinavir, ritonavir, saquinavir, telaprevir, telithromycin
CYP3A4 Inducers	
Strong inducers	avasimibe, carbamazepine, phenytoin, rifampin, St. John's wort

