18. Males who plan to father children within the projected duration of the study, starting with the screening visit through 120 days after the final dose of study treatment.
19. Major surgery within 28 days (or inadequate recovery from the toxicity or complications of the intervention) before the start of study treatment.

Note: If the participant had major surgery, the participant must have recovered adequately from the procedure and/or any complications from the surgery prior to starting study intervention.

20. Radiotherapy within 14 days of start of study treatment. Patient must have recovered from all radiation-related toxicities, not require corticosteroids, and not have had radiation pneumonitis. A 7-day washout is permitted for palliative radiation (i.e., \leq 14-day course of radiotherapy) to non-CNS lesions.
21. Patient currently receiving treatment with any medications that have the potential to prolong the QT interval and that cannot be either discontinued or substituted with a different medication prior to starting study treatment.

22. Patient currently receiving treatment with strong cytochrome P450 (CYP)3A4 inhibitors or inducers should discontinue such treatment or be switched to a different medication prior to starting study treatment.
23. Current participations in another study of an investigational agent or investigational device within 4 weeks prior to the first dose of study.
24. Any illness, medical condition, organ system dysfunction, or social situation, including mental illness or substance abuse, deemed by the investigator to be likely to interfere with a patient's ability to sign informed consent, adversely affect the patient's ability to cooperate and participate in the study, or compromise the interpretation of study results.

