7.6.4. Prohibited Concomitant Therapies and Drugs

Medications or vaccinations specifically prohibited in the exclusion criteria are not allowed during this trial. If there is a clinical indication for any medication or vaccination specifically prohibited during the study, discontinuation of study treatment or vaccination may be required. The investigator should discuss any

questions regarding this with the Sponsor. The final decision on any supportive therapy or vaccination is at the discretion of the investigator. However, the decision to allow the subject to continue to receive study treatment requires the mutual agreement of the investigator, the Sponsor, and the subject. (See Appendix [6](#))

Subjects are prohibited from receiving the following therapies during the Screening and Treatment Phase of this study:

- Antineoplastic systemic chemotherapy or biological therapy
- Immunotherapy not specified in this protocol
- Chemotherapy not specified in this protocol
- Investigational agents other than pembrolizumab or FLX475
- Radiation therapy

Note: Radiation therapy to a symptomatic solitary non-target lesion or to the brain may be allowed at the investigator's discretion.

- Live or live attenuated vaccines within 30 days prior to the first study dose and during participation in the study.

Note: Killed vaccines are allowed.

- Systemic glucocorticoids are permitted only for the following purposes:
 - To modulate symptoms of an AE that is suspected to have an immunologic etiology
 - As needed for the prevention of emesis
 - Premedication for IV contrast allergies
 - Short-term oral or IV use in doses >10 mg/day prednisone equivalent for COPD exacerbations
 - For chronic systemic replacement not to exceed 10mg/day prednisone equivalent
 - In addition, the following glucocorticoid use is allowed:
 - For topical use or ocular use
 - Intraarticular joint use
 - For inhalation in the management of asthma or chronic obstructive pulmonary disease.

The use of physiologic doses of corticosteroids may be approved after consultation with the Sponsor.

Note: Inhaled steroids are allowed for management of asthma or seasonal allergies. The use of prophylactic corticosteroids to prevent allergic reactions (e.g., IV contrast dye or transfusions) is permitted

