If the investigator determines that a subject requires any of the aforementioned treatments for any reason, study intervention FLX475 and pembrolizumab must be discontinued. If a subject receives additional anticancer therapies, this will be judged to represent evidence of Progressive Disease (PD), and study treatment will be discontinued. These subjects should complete all End-of-Treatment assessments and continue to be followed for survival in the Follow-up Phase unless they withdraw consent or are lost to follow-up.

All treatments that the investigator considers necessary for a subject's welfare may be administered at the discretion of the investigator in keeping with the community standards of medical care.

All concomitant medication will be recorded on the eCRF, including all prescription, over-the-counter products, herbal supplements, and IV medications and fluids. If changes occur during the study period, documentation of drug dosage, frequency, route, and date should also be included on the eCRF.

All concomitant medications administered during SAEs or events of clinical interest (ECIs) are to be recorded on a SAE form. SAEs and ECIs are defined in Section [9.2.2](#).

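### Protocol 7.6.4 lets study treatment continue by agreement when a QT-prolonging or strong CYP3A4 drug is given; Appendix 6 requires it to stop

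*Protocol*

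**What the plan says.** Protocol 7.6.4 opens with its scope: "Medications or vaccinations specifically prohibited in the exclusion criteria are not allowed during this trial". If such a product is clinically indicated, "discontinuation of study treatment or vaccination may be required". It then says that "the decision to allow the subject to continue to receive study treatment requires the mutual agreement of the investigator, the Sponsor, and the subject", and the cross-reference to Appendix 6 follows directly.

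Appendix 6 states: "Subjects who receive any of these medications during the Treatment Phase must discontinue study treatment". Its two tables cover QT-prolonging drugs (Table A6:1) and strong CYP3A4 inhibitors or inducers (Table A6:2).

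Further on, 7.6.4 gives a bulleted list introduced as therapies that subjects may not receive. After the list comes a second mandatory statement, for any subject who "requires any of the aforementioned treatments for any reason, study intervention FLX475 and pembrolizumab must be discontinued". The list also contains items that are allowed. One is systemic glucocorticoids for stated purposes, the first being "To modulate symptoms of an AE that is suspected to have an immunologic etiology". Another is a note that radiation to a symptomatic solitary non-target lesion or to the brain may be allowed at the investigator's discretion.

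**The concern.** An investigator whose subject needs a drug in Table A6:1 or A6:2 finds two answers. Section 7.6.4 makes stopping a possibility and gives a route to continue. Appendix 6, to which that section points, makes stopping compulsory.

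The drug classes are not incidental. Section 3.2 names QTcF prolongation as the only dose-related effect of FLX475 seen clinically. Section 3.1.3.2.2 reports one dose-limiting QTc event in each of the 75 mg and 100 mg monotherapy cohorts, both in subjects with confounding factors. Section 9.2.2 makes QTcF prolongation an event of clinical interest. Section 3.1.3.1.2 says CYP3A4 is likely responsible for FLX475 metabolism, and Section 3.1.3.2.2 predicts QTcF prolongation at higher exposures.

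At stake is whether subjects in the same situation are handled alike on a safety matter. The SAP's summaries of reasons for end of treatment (5.1.1) and of exposure (8) would also depend on which statement a site followed. Section 17.4 carries Section 7.6 into the extension part, so the conflict continues there.

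**Working it through.** The documents give no figure on this point, so the check is a comparison of text.

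**Step 1: do the two statements cover the same drugs?** The opening of 7.6.4 applies to what the exclusion criteria prohibit. Exclusion criterion 21 (Section 6.2) begins "Patient currently receiving treatment with any medications that have the potential to prolong the QT interval", and criterion 22 begins "Patient currently receiving treatment with strong cytochrome P450 (CYP)3A4 inhibitors or inducers". These are the classes in Tables A6:1 and A6:2 respectively. The scopes overlap on both.

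**Step 2: what does each statement require?**

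| Place | Stopping study treatment | Route to continue |
|---|---|---|
| 7.6.4, opening | Possible | Agreement of investigator, Sponsor and subject |
| Appendix 6 | Compulsory | None stated |
| 7.6.4, closing | Compulsory for the treatments it refers back to | None stated |

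The first two rows cannot both hold for a subject given a drug in either table.

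**Step 3: does any text rank them?** No. The cross-reference in 7.6.4 takes the reader from the permissive statement to the mandatory one without saying that either yields. Where the protocol intends an exception to a stop, it writes one. Table 7.3:1 attaches an exception after consultation to its Grade 4 rule, and Appendix 5 does the same for confirmed progression by iRECIST. The Appendix 6 sentence has nothing similar.

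**Step 4: what does the closing sentence of 7.6.4 refer back to?** The list just before it holds prohibited items (for example, chemotherapy not specified in the protocol) and allowed items (the glucocorticoid purposes and the radiation note). The sentence excludes none of them and applies whatever the reason. Taken literally, steroids for a suspected immune-related event would end both drugs. Section 7.3.2 says that most such events can be managed by interrupting pembrolizumab and giving corticosteroids. Table 7.3:3 directs corticosteroids with pembrolizumab only withheld for, among others, Grade 2 nephritis and Grade 2 AST/ALT or bilirubin elevation. The literal reading conflicts with both.

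This fourth step rests on 7.6.4 alone. Appendix 6 lists no corticosteroids.

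**The case against.** **The specific statement governs the general one.** On this view Appendix 6, as the detailed list, simply overrides 7.6.4. The argument is weak, because 7.6.4 cites Appendix 6 immediately after describing continuation by agreement. A site could as easily take the agreement as the exception to the appendix.

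**The closing sentence of 7.6.4 plainly means the prohibited therapies.** This has force. The list is introduced as prohibited therapies, the steroid bullet states its permitted purposes, and the radiation note is explicit. The literal reading would also catch topical and inhaled steroids, which the authors can hardly have meant. Immune-related events have their own instructions in Table 7.3:3. The steroid and radiation part is therefore a secondary drafting point that depends on a literal reading. The conflict with Appendix 6 does not depend on it.

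**A reader might infer that a compulsory stop prevents response from being assessed and so threatens the ORR.** The documents do not support this. Section 7.4 says that stopping treatment is not withdrawal from the study, and that subjects who stop without progression continue tumor assessments on the same schedule. Sections 8.4.3 and 9.1.2.3 ask for every effort to do so. Protocol 11.4.2 and SAP 12.1 run best overall response to progression or to the last evaluable assessment before events such as new anticancer therapy, death or loss to follow-up. Stopping study drug is not among the events named. A response seen and confirmed after stopping can still count. Lost exposure might lower the chance of response, but the documents offer nothing to measure that. It is true that one responder can matter near the 80% posterior bar, but that holds for any cause of a lost responder and does not measure this conflict.

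**Conclusion.** The protocol contains two incompatible discontinuation statements for QT-prolonging drugs and strong CYP3A4 inhibitors or inducers, and no order of precedence. This conclusion rests on the wording of 7.6.4, Appendix 6 and exclusion criteria 21 and 22, and needs no assumption about intent. The closing sentence of 7.6.4, with permitted uses inside the list it refers to, is a lesser fault that holds on a literal reading.

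The size cannot be computed: how many subjects would receive a listed drug is not given. The consequence is that sites can handle the same event differently where QTcF safety is concerned. It does not extend to how response is ascertained. The point deserves correction, and it does not undermine the design.

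**What to change.** The sponsor should reconcile the opening of 7.6.4, its closing sentence and Appendix 6, and align all three with Section 7.3.2 and Table 7.3:3. One statement should govern each class: QT-prolonging drugs, strong CYP3A4 inhibitors or inducers, systemic glucocorticoids, and radiation. The permitted glucocorticoid and radiation uses should be moved out of the list to which the mandatory-stop sentence refers, or expressly exempted from that sentence if that is what is meant. Which statement should prevail is a clinical decision for the sponsor, and none is proposed here.

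The cost is a protocol clarification. Sample size, endpoints and analyses do not change.
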